## 8 Statistical Considerations

This section describes the statistical approach for each comparison of active treatment versus its concurrent and eligibility matched placebo comparator group.

### 8.1 Statistical and Analytical Plans

There will be a formal Statistical Analysis Plan (SAP). This SAP will provide detailed descriptions of all primary, secondary, and sensitivity analyses, all interim and final decision thresholds, and all required documentation to ensure the reproducibility of statistical analyses. The SAP will be finalized prior to the first interim analysis for the platform, and arm-specific SAP amendments (if required) will occur before the first interim analysis involving that arm. The finalized SAP will take precedence and override the statistical considerations described in this section of the master protocol (i.e., Statistical Considerations).

### 8.2 Analysis Datasets

All sub studies conducted under this protocol will use a modified intention-to-treat (mITT) approach for primary analyses. The mITT analysis dataset (i.e., the “full analysis set”) will include all randomized participants according to the treatment assigned at randomization regardless of subsequent compliance or protocol violations, with the following exceptions: Participants who do not receive study drug will be excluded from the mITT analysis dataset. Those patients who were randomized and found to be ineligible will be excluded from the mITT analysis dataset. The safety analysis dataset will be produced, which will consist of all participants who received at least one dose of study medication grouped by the drug received. No statistical hypothesis tests nor other statistical inferences will be made using the safety analysis dataset unless requested by the DSMB.

Per protocol analyses will not be routinely performed but may be conducted as sensitivity analyses to support the mITT analysis. A key monitoring data point is the count of participants who are randomized and included in the ITT dataset but have not received study drug. We expect this to be less than 5% among participants who have completed the study. If this becomes greater than 5% during the trial, study leadership will meet with study teams to explore and mitigate this issue and will ensure the number of patients who receive study drug meets the original enrollment goals. We will report results for both the mITT (primary) and ITT datasets.

### 8.3 Statistical Modeling

The effect of each study agent versus matching placebo will be quantified using an odds ratio. The odds ratio represents the treatment effect on the odds of greater values of the primary outcome (i.e., improved lung function through 28 days, as measured by oxygen-free days). Based on the behavior of similar outcomes in prior trials, we anticipate the distribution of the primary outcome to be irregular, with peaks around -1 to 0 and between 22 and 28 days. Thus, we will use a flexible semi-parametric approach for the primary outcome analysis. Estimation and inferences about the odds ratio will be made using Bayesian proportional odds (PO) logistic regression methods. For each study agent, the comparator group will consist of participants concurrently randomized to receive placebo who also meet the inclusion and exclusion criteria for that agent.

The general form of the PO model can be written in terms of the covariates  $X$  and an outcome variable  $Y$ , where probabilities of outcome value  $y$  or greater  $\text{Pr}(Y \geq y|X) = \text{expit}(\alpha_y + X\beta)$  where  $\alpha_y$  is the intercept for outcome value  $y$  and expit is the logistic (inverse logit) transformation and  $X$  contains baseline covariates and treatment.  $\beta$  represents the log odds ratio (OR) associated with

the effects of covariates and group assignment. Specifically, the odds ratio represents the relative effect of treatment versus placebo on the odds  $\text{Pr}(Y \geq y|X)/(1 - \text{Pr}(Y \geq y|X))$ , for any value  $y$ .

#### **8.4 Loss to Follow-up, Censoring, and Intercurrent Events**

Participants who withdraw consent prior to data collection, or for whom there is no partial information about the primary outcome, will not be excluded from analysis. We will strive to avoid loss to follow-up by making repeated attempts to contact participants or otherwise retrieve participant records. If loss-to-follow-up cannot be avoided, and the information needed to compute the primary endpoint is partially known (i.e., censored), we will use likelihood-based methods to account for this censoring. For example, if a study participant received supplemental oxygen every day during a 10-day period after randomization, but is then lost to follow-up, the primary outcome is only partially known (i.e., OFDs  $\leq 18$  in this example). The PO model provides a convenient mechanism to account for this and other types of censoring using a likelihood-based approach. For observations that are fully observed, the log likelihood contribution is  $l(\alpha, \beta; y, x) = \log \text{Pr}(Y = y|X = x)$ . For observations that are left censored at  $y$  (e.g.,  $\leq 18$  OFDs) observations, the log likelihood contribution is  $l(\alpha, \beta; y, x) = \log \text{Pr}(Y \leq y|X = x)$ . The latter is conveniently computed by substituting  $1 - \text{expit}(\alpha_y + x\beta)$ . Censored observations on the primary outcome due to loss of follow-up, including observations that are censored with respect to both oxygen requirement and mortality, will be handled using this mechanism.

All primary analyses will be implemented using the mITT analysis dataset as described above (see *Analysis Datasets*). The intercurrent event of death will be coded as a special value in the primary outcome (i.e., composite strategy). Censoring in the primary outcome will be modeled using the likelihood method described above. No other intercurrent events will affect the primary outcome assessment (i.e., treatment policy strategy).

#### **8.5 Model Prior and Bayesian Computation**

A flat prior distribution will be used for all PO model parameters. This ensures that the estimate of the primary estimand will be free of influence from an informative prior, and the Bayesian estimate will be identical to the maximum likelihood estimate. The posterior distribution for the log odds ratio will be approximated using the Laplace method. Use of a flat prior ensures the Laplace-approximated posterior distribution is identical to the asymptotic sampling distribution of the maximum likelihood estimate; in both cases a normal distribution centered at the estimate with variance-covariance equal to the inverse Hessian of the log likelihood function. All statistical inferences about the odds ratio will be made using this method. Statistical uncertainty about supplementary estimands (e.g., treatment difference in the median of the primary outcome) will be quantified using the delta method. We feel there is insufficient information, specific to the study agents and primary outcome, upon which to justify a more informative prior. The flat prior approach ensures that Bayesian inferences regarding the efficacy of study agents are based exclusively on the data collected in the ACTIV-4 Host Tissue trial.

#### **8.6 Analysis of Primary Outcome**

##### **8.6.1 Primary Analysis**

The effect of each study agent versus matching placebo will be quantified using an odds ratio, which quantifies the treatment effect on the odds of greater values of the primary outcome. Estimation and inference about the primary estimand (and supplementary estimands) will be implemented using Bayesian PO logistic regression methods, adjusting for the active drug vs placebo indicator variable, age group (18-30, 31-65, >65 years), sex at birth, baseline WHO COVID

ordinal outcome score at baseline. Evidence for efficacy will be quantified using the posterior probability that the active agent versus placebo odds ratio is greater than one (i.e., treatment is associated with greater oxygen free days at day 28). This is denoted the “efficacy probability” or  $P(\text{OR} > 1|\text{Data})$ , where OR represents the odds ratio, and Data represents the available outcome data. The posterior probability for inferiority/harm is defined as  $P(\text{OR} \leq 1|\text{Data})$ . The primary analysis will be implemented separately for each study agent, where the matching placebo group will consist of concurrently randomized participants meeting the inclusion and exclusion criteria for that agent. The primary and supplementary estimands will be presented with 95% credible intervals. While we do not anticipate missing covariate data.

### 8.6.2 Planned Interim and Final Analyses, Early Stopping, and Type-I Error Control

At the final analysis (only) for each arm, efficacy will be indicated if the posterior probability for efficacy exceeds a common threshold. For studies under this master protocol, the efficacy threshold will be selected using statistical simulation to ensure a type-I error probability of 2.5% for each study agent.

Two planned interim analyses will occur separately for each study arm when the number of participants with complete 28-day follow-up (or were deceased, withdrawn, or lost-to-follow-up by day 28) reaches 33% and 67% of maximum enrollment for that arm. Interim analyses will be executed by unblinded personnel only. Participant records that inform the primary outcome must undergo monitoring prior to interim (and final) analysis. At each interim analysis, a study arm may be stopped early if there is evidence for inferiority/harm. The trial will be stopped early if the posterior probability for inferiority/harm exceeds 0.95.

### 8.6.3 Supplementary Efficacy Estimands

The PO model is attractive for the analysis of ordinal and quantitative response variables, such as the primary outcome, because they directly model the cumulative distribution function from which the mean, median, other percentiles, and cumulative probabilities of the primary outcome, stratified by treatment group, are easily derived. In addition to the odds ratio, the effects of treatment versus placebo will be quantified using the difference in mean, difference in median, and differences in clinically relevant proportions associated with the primary outcome (e.g., mortality at day 28:  $\text{Pr}(Y = -1|X)$ , and oxygen requirement every day until day 28:  $\text{Pr}(Y = 0|X)$ ). These important and clinically meaningful supplementary estimands will be used to describe and communicate the treatment effect. The posterior distribution for each of the supplementary estimands is readily computed using standard Bayesian methods.

### 8.6.4 Sensitivity and Supplementary Analyses

Sensitivity and supplemental analyses will be implemented at the final analysis.

The *proportional odds assumption* of the PO model specifies that the effect of treatment on the odds that  $Y \geq 3$  (measured as an odds ratio versus placebo) is the same relative effect as for  $Y \geq 4$ . However, even when the PO assumption is strongly violated, the estimated OR remains a simple function of the Wilcoxon-Mann-Whitney U-statistic, namely the probability that a randomly chosen patient on treatment B has a higher response than a randomly chosen patient on treatment A, the *probability index* or *concordance probability*. Thus, statistical testing based on the odds ratio, as estimated using the PO model, are robust to violations of the PO assumption and provide a reasonable global assessment of treatment effectiveness. However, derived quantities such as the difference in means may be more sensitive to violations of the PO assumption. Deviations from

proportional odds will be examined by separately estimating the odds ratio for each possible dichotomization (that preserves ordering) of the primary outcome (e.g., alive versus dead at day 28, alive and oxygen free for at least 10 days at day 28 versus alive and oxygen free for fewer than 10 days or dead at day 28, etc.).

Analysis of partially observed or missing outcome data requires assumptions regarding the mechanism by which censoring and missing values arise. The likelihood method described above, and other similar methods such as multiple imputation assume that missing values occur at random (i.e., missing at random or MAR). However, because censored and missing values cannot be observed, assumptions about the missingness mechanism are not verifiable. In order to assess the sensitivity of study findings to violations of this assumption, we will conduct additional sensitivity analyses by reproducing the primary analysis under alternative assumptions regarding the mechanism for missing values. Specifically, we will perform sensitivity analyses that vary assumptions about the missing outcomes on the two treatment arms separately. These analyses will consider the following two scenarios 1) each partially observed primary outcome in the placebo group will be assumed to have taken the highest/best possible value, whereas each partially observed primary outcome in the intervention group will be assumed to have taken the lowest/worst possible value, and 2) each partially observed primary outcome in the placebo group will be assumed to have taken the lowest/worst possible value, whereas each partially observed primary outcome in the intervention group will be assumed to have taken the highest/best possible value. These analyses will be implemented using the primary analysis methodology, including an assessment of hypothesis testing outcomes.

Co-enrollment in other studies testing COVID-19 therapeutics may occur. Co-enrollment may affect the treatment effect estimates if there is effect modification associated with co-enrollment. We expect co-enrollment to occur in fewer than 5% of patients enrolled in the trial. However, because the decision to co-enroll is not affected by the treatment assignment in ACTIV-4 Host Tissue, co-enrollment will not favor any particular treatment. In addition, due to its rarity, we expect co-enrollment to have little impact on the estimated treatment effects, even when there is effect modification.

Differential treatment effect, also referred to as heterogeneity of treatment effect, refers to differences in efficacy as a function of pre-existing patient characteristics such as baseline variables. This is often assessed by forming subgroups or using an interaction analysis. Supplemental interaction analyses will be implemented to examine the potential for differential treatment effect. Differential treatment effect will be examined in strata defined by (but not limited to) respiratory support category at enrollment, status of co-enrollment in an open label clinical trial of antiplatelet agents (ACTIV-4a), age category, SARS-CoV-2 vaccination status, and passive immunity status, co-enrollment in other studies, and concomitant use of study drug and other medications during the study drug administration period. These analyses will be implemented using a modified version of the primary analysis method, where the treatment effect will be estimated separately for each level of the stratification variable. Stratum-specific treatment effect estimates will be presented with 95% Bayesian confidence interval. No formal hypothesis testing will be implemented for these analyses. Studies under this master protocol will be sized only for assessing efficacy using the primary analysis. Thus, there may be inadequate power to examine differential treatment.

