### **7.7.5 Baseline variable collection**

Baseline is defined as the patient's status at randomization. Physiological measurements and laboratory results obtained in the 24 hours prior to randomization may contribute to baseline data. The baseline study-specific blood draws may be completed at any time between consent and the first dose of study medication. The following information will be obtained to reflect the patient's baseline status:

1. Confirmation of informed consent for trial participation
2. Confirmation of inclusion/exclusion eligibility criteria for trial participation

3. Confirmation of the participant not being pregnant including a study-dedicated pregnancy test for women of childbearing potential (WOCBP).
  - a. WOCBP are defined as any female who has experienced menarche, has not undergone surgical sterilization (hysterectomy, bilateral salpingectomy, or bilateral oophorectomy), and has not experienced menopause
  - b. Postmenopausal women, defined as someone who has gone through menopause, do not have to take a pregnancy test.
4. Admission data: date and time of presentation, origin (home, skilled nursing facility, rehabilitation/long-term-acute care hospital, nursing home, outside hospital, outside ICU), location at enrollment (ED, hospital ward, ICU)
5. Sociodemographics (such as age, sex, race, ethnicity, height, weight, poverty index)
6. Study-specific blood draws (AngII, Ang(1-7), ACE and ACE2, NTproBNP and Troponin) as indicated for each investigational agent in the Ancillary Biomarker Appendix (Appendix C: Minimum Biological Specimen collection).
7. Comorbidities such as: AIDS, Leukemia, Malignant Lymphoma, Hemiplegia, Cerebrovascular Disease, Prior Myocardial Infarction, Congestive Heart Failure, Peripheral Vascular Disease, Dementia, COPD, Connective Tissue Disease, Peptic Ulcer Disease, History of Hypertension, HIV positive (without AIDS), Alcoholism, Coronary Artery Disease, Solid Tumor, Liver Disease, Diabetes Mellitus, Chronic Kidney Disease
8. Acute signs and symptoms such as: altered mental status, acute hypoxemic respiratory failure, liver function tests, renal function, coagulation studies, chest imaging results
9. Sequential Organ Failure Assessment (SOFA)
10. Chronic use of medications, such as: corticosteroids, ACE inhibitors, angiotensin receptor blockers, non-steroids anti-inflammatory drugs, others

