### **7.7.6 Assessments between hospital presentation and hospital discharge**

1. On days of study medication administration (before study administration in those arms where study drug is not an infusion)
  - a. Adverse events of any grade severity present prior to the infusion or medication administration
  - b. Start and stop (or administration time if oral) times of the infusion of the investigational agent/placebo- and restart time if medication stopped for hypotension
  - c. Starting dose of study medication administration
  - d. New adverse events of grade 3-4 severity during and after study medication administration
2. Recording of specifics of study treatment according to assigned arm
3. Daily laboratory assessments as part of routine clinical care (CBC, BMP, LFTs, PT/PTT/INR, D-dimer and CRP).

4. Daily vital signs (including blood pressure), secondary outcomes and safety assessments. In the fostamatinib arm a daily CBC and liver function tests will also be performed.
5. Study-specific blood draws (AngII, Ang(1-7), NT-ProBNP and Troponin) as indicated for each investigational agent in the Ancillary Biomarker Appendix (Appendix C: Minimum Biological Specimen collection).
6. Targeted concomitant medications administered daily in the hospital including remdesivir, Corticosteroids, antiplatelet/anticoagulation, convalescent plasma, monoclonal Ab's, antibacterial agents, antiviral agents against SARS-CoV-2, ACEI's, ARBs, beta blockers.
7. Date and time of first receipt of supplemental oxygen, high-flow nasal cannula, non-invasive ventilation, invasive mechanical ventilation, vasopressors, and extracorporeal membrane oxygenation (if applicable)
8. Date and time of final receipt of supplemental oxygen, high-flow nasal cannula, non-invasive ventilation, invasive mechanical ventilation, vasopressors and extracorporeal membrane oxygenation (if applicable)
9. Pulmonary embolism, systemic arterial thromboembolism, myocardial infarction, or ischemic stroke at hospital discharge or 28 days, whichever occurs first
10. Date and time of first ICU admission
11. Date and time of final ICU discharge
12. Data and time of hospital discharge

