## 22.5 Fostamatinib-specific safety considerations and potential medication interactions

Fostamatinib has a consistent safety profile, with the most common adverse reactions ( $\geq 5\%$  and more than placebo) being diarrhea, hypertension, nausea, respiratory infection, dizziness, ALT/AST increase, rash, abdominal pain, fatigue, chest pain and neutropenia. Warnings and precautions included in the US product label include hypertension, elevated liver function tests, diarrhea, neutropenia, and embryo-fetal toxicity.

- Fostamatinib must be discontinued in case the patient becomes pregnant.
- Concomitant use with strong CYP3A4 inhibitors with fostamatinib will increase exposure to the active metabolite R406 and may result in increased risk of adverse reactions. **Therefore, patients that cannot have strong CYP3A4 inhibitors held should be excluded from the Fostamatinib arm.** Strong CYP3A4 inhibitors that should exclude patients from the fostamatinib arm include: Atazanavir, Certinib, Clarithromycin, Cobicistat and cobicistat-containing coformulations, Idelalisib, Indinavir, Itraconazole, Ketocanazole, Levoketoconazole, Lonafarnib, Lopinavir, Mifepristone, Mibefradil, Nefazodone, Nelfinavir, Ombitasvir-paritaprevir-ritonavir plus dasabuvir, Posaconazole, Ribociclib, Ritonavir, Saquinavir, Telithromycin, Troleandomycin, Tucatinib, Voriconazole. Novel strong CYP3A4 inhibitors may be released after the writing of this protocol appendix. If you anticipate the patient will require a strong CYP3A4 inhibitor that is not included in the list above, please reference this regularly updated list: <https://drug-interactions.medicine.iu.edu/MainTable.aspx>

Fostamatinib itself is a weak CYP3A4 inhibitor and will result in a modest ( $\sim 1.25$  fold) increase in CYP3A4 substrates. Medications processed (activated or deactivated) by the CYP3A4 enzyme are here referred to as CYP3A4 substrate medications. Concomitant use of CYP3A4 substrate medications with Fostamatinib will modestly decrease the processing of the CYP3A4 substrate medication. If possible, CYP3A4 substrate medications should be held or have another medication substituted for them. Due to its modest effects, concomitant use of CYP3A4 substrate medications is not an exclusion criterion for this trial. However, investigators should carefully consider inclusion of patients taking CYP3A4 substrate medications with narrow therapeutic windows and should monitor closely for toxicities.

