### **Hypertension:**

[figure not shown]
Blood pressure  $> 140/90$  should be treated with antihypertensives per usual care.

**During the inpatient hospitalization:** If systolic BP remains  $> 160$  mmHg or diastolic BP  $> 100$  mmHg or higher despite antihypertensive therapy, interrupt study drug. When restarting study drug

once BP is below 160 mmHg systolic and 100 mmHg diastolic, drug dose should be reduced to 100 mg twice daily or matching placebo for the remainder of the study.

- **At the time of Hospital discharge:** Patients **still on study drug** at the time of hospital discharge will have the following study procedures performed (see [Figure 3](#)):

**Figure 3. Schematic overview of blood pressure considerations and procedures performed for patients still on study drug at the time of hospital discharge**

- 1) Those with SBP < 160 mmHg and DBP < 100 mmHg will continue on study drug at the inpatient dose and have no further BP measurements for study purposes
- 2) Those with SBP  $\geq$  160 mmHg or DBP  $\geq$  100 mmHg at the time of hospital discharge will have study medication stopped and undergo the following repeat testing:

- 1) 7 (+/-2) days after post-hospital discharge a repeat blood pressure will be obtained.
  - a. If the SBP is < 160 mmHg and DBP is < 100 mmHg no further BP monitoring will be performed for study purposes
  - b. If the SBP is  $\geq$  160 mmHg or the DBP is  $\geq$  100 mmHg a follow-up will be performed in 7 (+/-2) days after the prior visit
    - i. At the repeat visit if the SBP is < 160 mmHg and DBP is < 100 mmHg no further BP monitoring will be performed for study purposes
    - ii. At the repeat visit if the SBP is  $\geq$  160 mmHg or DBP is  $\geq$  100 mmHg study guidance will recommend BP recheck by a healthcare provider

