
Co-enrollment in other studies testing COVID-19 therapeutics may occur. Co-enrollment may affect the treatment effect estimates if there is effect modification associated with co-enrollment. We expect co-enrollment to occur in fewer than 5% of patients enrolled in the trial. However, because the decision to co-enroll is not affected by the treatment assignment in ACTIV 4 Host Tissue, co-enrollment will not favor any particular treatment. In addition, due to its rarity, we expect co-enrollment to have little impact on the estimated treatment effects, even when there is effect modification.

Differential treatment effect, also referred to as heterogeneity of treatment effect, refers to differences in efficacy as a function of pre-existing patient characteristics such as baseline variables. This is often assessed by forming subgroups or using an interaction analysis. Supplemental interaction analyses will be implemented to examine the potential for differential treatment effect. Differential treatment effect will be examined in strata defined by (but not limited to) respiratory support category at enrollment, status of co-enrollment in an open label clinical trial of antiplatelet agents (ACTIV 4a), age category, SARS-CoV-2 vaccination status, passive immunity status, co-enrollment in other studies, and concomitant use of study drug and

other medications during the study drug administration period. These analyses will be implemented using a modified version of the primary analysis method, where the treatment effect will be estimated separately for each level of the stratification variable. Stratum-specific treatment effect estimates will be presented with 95% Bayesian confidence interval. No formal hypothesis testing will be implemented for these analyses. Studies under this master protocol will be sized only for assessing efficacy using the primary analysis. Thus, there may be inadequate power to examine differential treatment.

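### Odds ratios stratified by medication use during dosing are not randomised comparisons, and the protocol contradicts itself on WHO category 3 at baseline, which the primary covariate does not code

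*Protocol*

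**What the plan says.** **Medication stratifier.** Protocol 8.6.4 and SAP 6.5 say that differential treatment effect "refers to differences in efficacy as a function of pre-existing patient characteristics such as baseline variables". The list of strata that follows ends, in the protocol, with "concomitant use of study drug and other medications during the study drug administration period"; the SAP repeats it ("other medications during the study drug administration period"). For every listed variable "the treatment effect will be estimated separately for each level of the stratification variable". Results get 95% intervals, no test is made, and both documents warn of low power.

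Dosing begins after randomisation (Protocol 7.1: first dose within 6 hours) and runs up to 14 days in the fostamatinib arm (22.3). Protocol 22.5 lists the drug's common reactions as "being diarrhea, hypertension, nausea, respiratory infection, dizziness, ALT/AST increase" and others. Under 22.7, blood pressure above a stated level "should be treated with antihypertensives per usual care". Protocol 7.7.6 records "Targeted concomitant medications administered daily in the hospital including remdesivir, Corticosteroids" and further classes that include ACE inhibitors, ARBs and beta blockers. Protocol 7.7.5 already collects pre-randomisation use: "Chronic use of medications, such as: corticosteroids, ACE inhibitors, angiotensin receptor blockers", plus antivirals, immunomodulators, anticoagulants and antiplatelets received between presentation and randomisation.

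**WHO category 3 at baseline.** The text of Protocol 19.2 says some participants enter without oxygen therapy, in category 3. Table 3 in the same section says category 3 at baseline is not eligible. The Protocol summary describes the population as on oxygen therapy. Inclusion criterion 4 (6.1) accepts SpO2 below 92% on room air as one route to hypoxemia. Protocol 8.2 and SAP 4 remove randomised participants later found ineligible from the mITT set. SAP 6 codes the baseline WHO covariate as 4, 5 and 6-7. SAP 6.2 anticipates no missing covariate data and gives no rule for an unlisted level.

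**The concern.** **Medication stratifier.** Randomisation balances the groups overall and within levels of anything fixed beforehand. It does not balance them within levels of something that assignment can alter. The documents supply one such route: drug to hypertension to antihypertensive. If use also tracks prognosis, active and placebo users differ in prognosis, and so do active and placebo non-users. A stratum odds ratio could then be read as the drug's effect in that group when part of it is selection.

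**Category 3.** Membership of the primary analysis set, and the coding of one of its covariates, depend on which passage the analyst follows. If that is settled after unblinding, it is a discretionary choice in the primary analysis.

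**Working it through.** The plan gives no figure for either part, so there is none to reproduce. The sizes below rest on stated assumptions.

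**Part 1: stratifying on use during dosing**

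Inputs from the documents: 300 per group; placebo distribution of oxygen-free days (OFD) built to match the planning table (death 0.235, zero days 0.296, 22 or more days 0.19, mean 8.8). Assumed, because the documents give no values: covariate effects; an unmeasured course of illness with SD 1 on the logit scale; probability of use linked to that course by 0.5 to 1 log-odds per SD, in either direction; use of 30% on placebo and 40% or 50% on active. The model is proportional odds, adjusted for age group, sex and WHO level, with 4,000,000 simulated participants per scenario (log odds ratio SE about 0.003).

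| Stratifier | True overall OR | OR in each stratum |
|---|---|---|
| Use during dosing, 30% vs 50% | 1.00 | 0.85-0.92 or 1.08-1.17 |
| Use during dosing, 30% vs 40% | 1.00 | 0.92-0.96 or 1.04-1.09 |
| Use during dosing, 30% vs 50% | 1.53 | 1.32-1.42 or 1.66-1.80 |
| Receipt before randomisation | 1.00 | 0.99-1.01 |
| Receipt before randomisation | 1.53 | 1.53-1.55 |

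The direction follows the sign of the link. If sicker patients are likelier to be users and the drug adds users, the active users include milder cases and the remaining active non-users are the mildest, so both strata look better on drug. Reverse the link and both look worse. Because the shift is shared, the user/non-user ratio of odds ratios with no drug effect stays at 0.97-1.02 (30% vs 50%) or 0.99-1.01 (30% vs 40%).

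A simplified run (five-level outcome, no covariates, 30% vs 50%) gives users/non-users 1.08/1.09 at a link of 0.5 and 1.17/1.15 at a link of 1, with the overall OR at 1.00. A binary-outcome version that multiplies the odds of use by 1.5, 2 or 3 gives stratum ORs of about 1.06, 1.11 and 1.18. If treatment does not change use, there is no bias.

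At trial size, 30% vs 50% means 0.30 x 300 = 90 placebo and 0.50 x 300 = 150 active users, and 210 and 150 non-users. Stratum log odds ratio SEs are 0.19-0.25, so the largest shifts are 0.6-0.8 SE. In null trials a stratum's 95% interval excludes 1 in 10-14% (30% vs 50%, link of 1), 5-6% at 30% vs 40%, and 5-6% with pre-randomisation receipt. The user/non-user contrast excludes no difference in 5-6%.

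**Part 2: category 3**

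| Place | Category 3 at baseline |
|---|---|
| Protocol 19.2, text | some are enrolled |
| Protocol 19.2, Table 3 | not eligible |
| Protocol summary, Population | on oxygen, so implicitly out |
| SAP 6, covariate levels | no level, so implicitly out |
| Protocol 6.1, criterion 4 | possible through the room-air clause |

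No passage settles it. The SAP's precedence (Protocol 8.1) covers only the protocol's statistical section, not 6.1 or 19.2.

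For size, let a fraction f of 600 be category 3, assumed at 1%, 3% or 5% (6, 18 or 30 people). Treat Z with and without them as bivariate normal with correlation sqrt(1-f). The threshold 0.976 corresponds to z = 1.977. At the plan's stated power of 0.856 for an OR of 1.65, the mean of Z is 1.977 + 1.063 = 3.040, and 3.040 x sqrt(1-f) after dropping.

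| Share in category 3 | 1% | 3% | 5% |
|---|---|---|---|
| Conclusion differs, OR 1.65, power 85.6% | 1.9% | 3.3% | 4.5% |
| Same, if power is 93.5% | 1.0% | 1.9% | 2.6% |
| Conclusion differs, no effect | 0.5% | 0.8% | 1.0% |

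The 93.5% is a closed-form value for complete data. A simulation with category 3 assumed one log-odds better than category 4 gives 2.7%, 4.3% and 4.9% at OR 1.65, but its power was only 81-83%. The mean change in log odds ratio was within 0.003.

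**The case against.** **Part 1.** This is one item in an untested supplementary list. The list exists to examine differential effect, and that contrast is essentially undistorted. The 10-14% rate needs a 20-point shift in use and a strong link to prognosis, neither of which any document supplies; at a 10-point shift it is no worse than with the fix. The only documented route runs through antihypertensives; other co-medication is chosen by blinded clinicians. Concurrent exposure is a fair descriptive interest, given the interactions in Protocol 22.5. All of this stands and limits the weight. It does not turn the stratum odds ratios into randomised comparisons, and those are what the plan will present with intervals.

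A reader might infer that the analysis would create a false difference between users and non-users, or affect the primary conclusion. Neither follows: the shift is shared by both strata, and the primary analysis does not use this variable. Nor is the co-enrolment stratifier at fault. Protocol 7.6 item 5 already ties it to co-enrolment documented before randomisation.

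**Part 2.** The summary, Table 3 and the SAP covariate levels agree, so the sentence in 19.2 may be leftover text. The room-air clause does not by itself contradict Table 3: Protocol 7.7.5 lets readings from the prior 24 hours contribute to baseline, so someone with a room-air reading may be on oxygen by randomisation. The opening of Protocol 6, which disclaims exclusions for severity, is general and weak evidence. Protocol 9.1 asks for eligibility to be confirmed before allocation is released. The planning table shows 0.000 at 28 OFDs, which hints at few such participants among the first 100 but does not prove it, since a category 3 participant may need oxygen later. These points suggest a small number; they do not remove the contradiction.

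The protocol also promises ITT results alongside mITT (8.2). That settles membership for the ITT set but not coding, because an ITT fit with the same covariate meets the same missing level.

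**Conclusion.** Both parts hold, with modest weight.

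**Part 1.** The plan departs from its own definition by stratifying on a post-randomisation variable. Under the assumptions above, both stratum odds ratios move together to about 0.85-0.92 or 1.08-1.17 when the true value is 1, and by less if use differs by 10 points. Use rates and link strengths are assumed. The harm is to interpretation of supplementary estimates only.

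**Part 2.** Protocol 19.2 contradicts itself, and the primary analysis has no rule for the case. A reader might infer that this biases the primary result. The documents and the calculations do not support that: there is no systematic shift, the number affected is not stated, and a change of conclusion in roughly 1-5% of trials at OR 1.65 is about what removing any 1-5% of the data would do. What remains is an avoidable ambiguity in who is analysed and how they are coded.

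The age band printed as 31-64 in SAP 11.1, against 31-65 in Protocol 8.6.1 and SAP 6, is clerical.

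**What to change.** 1. In Protocol 8.6.4 and SAP 6.5, define the medication stratifier by receipt at or before randomisation, using the data collected under Protocol 7.7.5. Keep any summary by use during dosing only if labelled descriptive and non-causal. The cost is that baseline receipt does not answer the concurrent-use question, so concurrent use can then only be described.
2. Reconcile the Protocol summary, inclusion criterion 4, the text of 19.2 and Table 3 on category 3. This review does not say which eligibility rule is right.
3. In the SAP, state one mITT rule, fixed blind to assignment, for any category 3 participant already randomised. Match the WHO covariate levels in SAP 6 to it for both the mITT and ITT fits, and report the blinded count. If category 3 is kept, its level may be sparse and may need merging with a neighbour.
4. Make the age band in SAP 11.1 match SAP 6.

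The work is wording plus one blinded count. It needs no new data and leaves the primary model terms and the 0.976 threshold unchanged.
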